7.3 Methods and Timing for Assessing, Recording, and Analyzing Safety Parameters

See Table 3.

7.4 Adverse Events and Serious Adverse Events

An adverse event (AE) is any untoward medical occurrence in a subject during participation in the clinical study or with use of the experimental agent being studied. An adverse finding can include a sign, symptom, abnormal assessment (laboratory test value, vital signs, electrocardiogram finding, etc.), or any combination of these regardless of relationship to participation in the study.

Unanticipated problems. The Office for Human Research Protections (OHRP) considers unanticipated problems involving risks to subjects or others to include, in general, any incident, experience, or outcome that meets **all** of the following criteria:

- Unexpected in terms of nature, severity, or frequency given (a) the research procedures that are described in the protocol-related documents, such as the IRB-approved research protocol and informed consent document; and (b) the characteristics of the subject population being studied;
- Related or possibly related to participation in the research (“possibly related” means there is a reasonable possibility that the incident, experience, or outcome may have been caused by the procedures involved in the research); and
- Suggests that the research places subjects or others at a greater risk of harm (including physical, psychological, economic, or social harm) than was previously known or recognized.

Serious adverse events (SAEs). A serious adverse event (SAE) is one that meets one or more of the following criteria:

- Results in death
- Is life-threatening (places the subject at immediate risk of death from the event as it occurred; includes a suicide attempt or drug overdose)
- Results in inpatient hospitalization or prolongation of existing hospitalization
- Results in a persistent or significant disability or incapacity
- Results in a congenital anomaly or birth defect

An important medical event that may not result in death, be life threatening, or require hospitalization may be considered an SAE when, based upon appropriate medical judgment, the event may jeopardize the subject and may require medical or surgical intervention to prevent one of the outcomes listed in this definition.

Unanticipated problems will be recorded in the data collection system throughout the study. Study staff will record all reportable events with start dates occurring any time after informed consent is obtained until 8 weeks (i.e., follow-up assessment after the last day of class participation). Each time participants attend classes, we will inquire about injuries due to study participation. At midpoint, endpoint, and at week 8 follow-up, study staff will administer the SAFTEE in order to inquire about the occurrence of AE/SAEs during the previous 8-10 weeks. SAEs related study participation will be followed for outcome information until resolution or stabilization.

Characteristics of an adverse event will include: a) relationship to study intervention, b) expectedness of SAEs, and c) event severity.

Relationship to Study Intervention

To assess relationship of an event to study intervention, the following guidelines are used:

1. Related (Possible, Probable, Definite)
 - a. The event is known to occur with the study intervention.
 - b. There is a temporal relationship between the intervention and event onset.
 - c. The event abates when the intervention is discontinued.
 - d. The event reappears upon a re-challenge with the intervention.
2. Not Related (Unlikely, Not Related)
 - a. There is no temporal relationship between the intervention and event onset.
 - b. An alternate etiology has been established.

Relatedness of SAEs

The Study PI and Independent Monitoring Committee will be responsible for determining whether an SAE is expected or unexpected. An adverse event will be considered unexpected if the nature, severity, or frequency of the event is not consistent with the risk information previously described for the intervention. The risk information to assess expectedness can be obtained from preclinical studies, the investigator's brochure, published medical literature, the protocol, or the informed consent document.

Expected AEs for this study include:

- Any event that may be reasonably anticipated to occur as a result of the study procedure (i.e., mild aches or pains following a yoga class)

Severity of Event

The following scale will be used to grade adverse events:

1. Mild: no intervention required; no impact on activities of daily living (ADL)
2. Moderate: minimal, local, or non-invasive intervention indicated; moderate impact on ADL
3. Severe: significant symptoms requiring invasive intervention; subject seeks medical attention, needs major assistance with ADL

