Written informed consent will be obtained at the baseline visit. Please see section 4.4 for more information about the consent procedures.

Screening—Phase 2

Following informed consent, all participants will complete an initial demographics questionnaire. In phase 2, prisoner participants will also complete an interview consisting of those measures that will be used to determine eligibility for participation.

For purposes of assessment of certain inclusion/exclusion criteria, a brief diagnostic interview will be used to assess current mania, psychosis, or active suicide risk (warranting referral to prison mental health treatment staff). A brief questionnaire (PARQ) will be used to determine whether a participant can safely engage in a moderate level of physical activity. If the

participant endorses an item of this measure (except for item 6 which refers to hypertension medications, which are permissible in this study), they will be ruled ineligible.

List of measures used to assess inclusion/ exclusion criteria:

- Physical Activity Readiness Questionnaire
- Novaco Anger Scale – Provocation Inventory
- MINI (Screening)

Enrollment—Phase 2

If a participant meets all inclusion/ exclusion criteria, he/she will be enrolled in the study at this baseline visit. Study eligibility will be determined and documented on the RCT inclusion/exclusion sheet.

Baseline assessments—Phase 2

Remaining baseline assessments are detailed in Table 3.

Randomization—Phase 2

Randomization will occur at the baseline visit after all assessments are completed. Participants may begin study classes within one week of randomization.

6.2.5 Blinding – Phase 2.

The following individuals will be blinded during the course of the study: [name], MPI; [name], Statistician; [name], Co-I; [name], Co-I.

The following individuals will not be blinded during the course of the study: [name], MPI; [name], Co-I; [name], Project Coordinator; study interventionists; study RA. Randomization will be conducted by the study RA and overseen by [name], Project Coordinator (see section 9.2.2 for more information on randomization).

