For all follow-up assessments, research staff will make every effort to conduct the assessment within one week before or one week after the exact due date of the assessment. However, because all data can be analyzed with modern statistical methods regardless of whether it was collected inside that window, RAs will still collect data if possible even if it is later than that two-week window. We will record optimum date for the assessment as well as the actual date of the assessment.

Participants will complete a brief assessment after each class that they attend.

In addition, all participants will be assessed at: baseline, 5 weeks (mid-intervention), 10 weeks (post-intervention), 14 weeks (yoga group participants only), and at 8 week follow-up. In addition to demographics, we will assess acceptability of the intervention conditions, safety of the yoga condition, anger and aggression, secondary outcomes (depression and anxiety symptoms, general functioning), potential intervention mechanisms of action (anger rumination, decentering, impulsivity), and other descriptive characteristics (trauma history, treatment utilization, physical activity levels).

In the event that a participant is released back into the community before they complete all of their study assessments, we will complete them in the community. We will aim to complete all of these follow-up assessments by telephone. However, there may be some circumstances that might make it difficult for a participant to complete the follow-up assessment by telephone (e.g., limited phone minutes, enrollment in a residential treatment program). In such cases, we will complete the follow-up assessment in person in our offices at Brown University or in the facility where the participant is located (e.g., residential treatment facility, with facility approval). Additionally, if a participant is transferred to another facility at RIDOC, we will complete their assessments at the other facility (e.g., Men's Maximum Security) with RIDOC approval.

Please see table 3 for a list of all assessments to be completed at each visit.

6.2.7 Completion/Final Evaluation - Phase 2

Even if prisoners drop out of study treatment, we will attempt to collect data at all assessment points if prisoners agree to it.

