7.2 Specification of Safety Parameters

Safety issues will be minimal in Phase 1 given that participation involves only a single focus group, no yoga classes, and no formal assessment of suicidality. However, should an issue arise (e.g., a voluntary report of suicide ideation), staff would manage it in the same way that they would manage it in Phase 2.

Please see Table 4 for a summary of safety issues, how they are assessed, when they are assessed, and relevant staff actions.

Table 4. Assessment and Management of Safety Issues, Summary, Phase 2

Safety Issue	How assessed	When Assessed in Phase 2	Relevant Research Staff Actions
Suicide or homicidal ideation	PHQ-9 Participant report to research staff	BL, wk5, wk10, wk18 Any point	Immediate clinical assessment as described in DSMP
Injuries due to yoga	Structured self-report	Weekly during first 10 weeks	Follow until resolution; may result in changes to yoga instructor manual
Other AEs	SAFTEE Participant report to research staff	BL, wk5, wk10, wk18 Any point	If related to study participation, follow resolution; potential changes to procedures particularly if AE is also unexpected

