Feasibility and Acceptability—Research Procedures	
Recruitment rate	Average of 6 enrolled per month
Retention rate	80% complete week 10 assessment; 70% complete wk. 18 assessment
Completion of items on assessment instruments	At least 90% of items are completed on each assessment instrument (so each will be valid).

9.5.2 Secondary/ Exploratory Outcomes.

In Phase 2, we will also examine change in key variables over time. This is an exploratory analysis.

Specifically, we will look at change over time the in the following variables. The primary outcome in a subsequent efficacy study is in **bold and underlined**. Secondary outcomes are in standard text. *Potential mechanisms are in italics*.

- **NAS-Provocation Inventory from BL to wk10**; BL to wk18.
- Aggression Questionnaire – Short Form, BL to wk10; BL to wk18.
- Number of behavioral infractions in Prison, BL to wk10; BL to wk18
- PHQ-9, BL to wk10; BL to wk18
- PROMIS Anxiety, BL to wk10; BL to wk18
- SF-12 physical health composite score, BL to wk10; BL to wk18
- SF-12 mental health composite score, BL to wk10; BL to wk18
- *Anger rumination scale, BL to wk10; BL to wk18*
- *Experiences Questionnaire, BL to wk10; BL to wk18*

- *Stroop Color and Word Test, BL to wk10; BL to wk18*

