3.2 Time Period and Frequency for Event Assessment and Follow-Up

Unanticipated problems will be recorded in the data collection system throughout the study.

Study staff will record all reportable events with start dates occurring any time after informed consent is obtained until 8 weeks (i.e., follow-up assessment after the last day of class participation). Each time participants attend classes, we will inquire about injuries due to study participation. At midpoint, endpoint, and at week 8 follow-up, study staff will administer the SAFTEE in order to inquire about the occurrence of AE/SAEs during the previous 8-10 weeks. SAEs related study participation will be followed for outcome information until resolution or stabilization.

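### The fixed 8-10 week SAFTEE look-back does not fit visits 5, 5 and 8 weeks apart, and leaves 3-5 weeks of the class period unasked when only week 10 is missed

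*Combined protocol and SAP*

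**What the plan says.** Protocol section 7.4 sets one recall period for all three follow-up administrations: "study staff will administer the SAFTEE in order to inquire about the occurrence of AE/SAEs during the previous 8-10 weeks". DSMP section 3.2 gives the same instruction, to "inquire about the occurrence of AE/SAEs during the previous 8-10 weeks".

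Table 4 (section 7.2) lists the SAFTEE at "BL, wk5, wk10, wk18", and Table 3 (section 6.1) agrees. Section 6.2.6 gives the visits as "baseline, 5 weeks (mid-intervention), 10 weeks (post-intervention), 14 weeks (yoga group participants only), and at 8 week follow-up". The 14-week contact is a qualitative interview for the yoga arm and carries no SAFTEE. What section 7.4 calls the week 8 follow-up is therefore week 18, eight weeks after classes end.

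Four other provisions bear on the point:

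- **Consent (section 6.2.4):** "Written informed consent will be obtained at the baseline visit".
- **Recording period (section 7.4):** "Study staff will record all reportable events with start dates occurring any time after informed consent is obtained until 8 weeks".
- **Visit window (section 6.2.6):** staff try to "conduct the assessment within one week before or one week after the exact due date of the assessment", and later data are still collected.
- **Retention target (table in section 9.5.1):** "80% complete week 10 assessment; 70% complete wk. 18 assessment".

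Section 9.1.2 requires start and stop dates, severity, functional impact and perceived cause for every event, by whatever route it is found. No section changes the look-back after a missed or late visit. None states how an event reported at two visits is to be handled.

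**The concern.** A recall window that does not follow the visit schedule can fail in two directions. If it is longer than the interval since the last interview, the same weeks are asked about twice, or weeks before the study are asked about. If it is shorter, some weeks are not asked about at all. A fixed 8-10 weeks against intervals of 5, 5 and 8 does the first when visits are attended and can do the second when a visit is missed or late.

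The second failure matters more, because a duplicate can be found afterwards and an event that was never elicited cannot. Safety is one of the primary outcomes in section 9.5.1, and the SAFTEE is a named measure for it. The target there is no related serious adverse events or injuries, so an unasked period can make the target look met when it was not. A related SAE also triggers the halting rule in section 9.4.2. The committee reports in DSMP section 7.6 must compare AE rates with expectation, which needs a defined period of observation.

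**Working it through.** **Inputs.** SAFTEE visits at weeks 0, 5, 10 and 18 (Tables 3 and 4). Look-back L = 8 to 10 weeks (section 7.4, DSMP 3.2). Consent at week 0 (section 6.2.4). Visit window of one week either side (section 6.2.6). N = 40, with retention targets of 80% at week 10 and 70% at week 18 (section 9.5.1). Weeks are counted from the baseline visit, Day 0 in Table 3.

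**Does 8-10 weeks follow from the schedule?** The intervals are 5 - 0 = 5, 10 - 5 = 5 and 18 - 10 = 8 weeks. The stated figure fits neither 5-week interval. Only its lower end matches the last one.

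**All visits attended on time.** A visit at week v covers weeks v - L to v.

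| Visit | Covered, L = 8 | Covered, L = 10 | Before consent | Already covered at prior visit |
|---|---|---|---|---|
| Week 5 | -3 to 5 | -5 to 5 | 3-5 weeks | none |
| Week 10 | 2 to 10 | 0 to 10 | none | 3-5 weeks |
| Week 18 | 10 to 18 | 8 to 18 | none | 0-2 weeks |

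There is no gap in this case. Recall weeks that fall within the study are 5 + 8 + 8 = 21 at L = 8 and 5 + 10 + 10 = 25 at L = 10. Against 18 weeks of follow-up, 21/18 = 1.17 and 25/18 = 1.39, an excess of 17%-39%.

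**Missed or shifted visits.** The gap is the time between the last completed SAFTEE and the start of the next window, (next visit - L) - last visit, or zero if that is negative.

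- Week 10 missed, weeks 5 and 18 done: (18 - 8) - 5 = 5 weeks, or (18 - 10) - 5 = 3 weeks. Weeks 5 to 8-10 are not asked about.
- Week 5 missed, week 10 done: (10 - 8) - 0 = 2 weeks, or (10 - 10) - 0 = 0.
- Weeks 5 and 10 missed, week 18 done: 10 weeks, or 8 weeks.
- No visit missed, week 10 held at week 9 and week 18 at week 19, both inside the window: (19 - 8) - 9 = 2 weeks, or (19 - 10) - 9 = 0.

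**How many participants.** The targets tolerate 0.20 x 40 = 8 missing week 10 and 0.30 x 40 = 12 missing week 18. If everyone who misses week 10 also misses week 18, nobody has the 3-5 week gap. If all 8 completed week 5 and return at week 18, 8 do. The range within the target is therefore 0 to 8 of 40.

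**With the window anchored to the last completed SAFTEE.** Nominal recall is 5, 5 and 8 weeks, with no overlap and nothing before baseline. After a miss it becomes 10 - 0 = 10 weeks (week 5 missed), 18 - 5 = 13 weeks (week 10 missed) or 18 - 0 = 18 weeks (both missed), and no gap is left if week 18 is completed.

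**The case against.** The strongest reply is that most of the mismatch does no harm. The recording rule in section 7.4 already excludes events that start before consent, and a baseline SAFTEE exists to compare against. Section 9.1.2 collects enough detail on each event to recognise a repeat, and section 10.3.2 provides weekly review of AE reports in a trial of 40. The safety target is zero related serious events or injuries, and counting one event twice cannot turn zero into one. This stands: overlap and pre-consent reach affect at most the descriptive counts.

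A reader might infer more than the documents support in four ways.

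- **A 33%-67% excess of recall.** This comes from 24-30 total recall weeks (3 x 8 and 3 x 10) over 18, but it includes the 3-5 pre-consent weeks, whose events are not recordable. It also measures weeks asked about, not events.
- **Eight participants each with 3-5 unasked weeks.** Eight is a ceiling and needs weeks 5 and 18 both completed. Someone who completes week 5 and misses both later visits has 18 - 5 = 13 unasked weeks, which no wording recovers.
- **A gap after any missed visit.** Missing only week 5 leaves 0-2 weeks, and none at L = 10.
- **No other inquiry in the gap, or none but the SAFTEE in health education.** Spontaneous reports are taken at any time in both arms (section 9.1.2), the PHQ-9 screens for suicidality at scheduled visits (Table 4), and section 7.1 monitors need for services at each contact. After-class injury questions also continue. Section 9.1.2 limits these to yoga and section 7.4 does not, so the documents conflict on whether health education participants are asked.

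These sources reduce the gap but do not close it. None is a general, structured AE inquiry, and after-class questions reach only those who attend. It is also fair to say that the form and the manual of procedures are not in the documents and may carry different wording. Late data collection, telephone follow-up after release and assessment after treatment dropout (sections 6.2.6, 6.2.7 and 8) should make isolated misses less common.

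**Conclusion.** The concern holds as a mismatch between a stated recall rule and the visit schedule, with one consequence that other provisions do not repair. A participant who misses only week 10 has 3-5 weeks of the class period without SAFTEE inquiry. Between 0 and 8 of 40 could be in that position within the retention target. Visits at weeks 9 and 19, both permitted, leave up to 2 weeks uncovered with nothing missed.

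The overlap and the 3-5 week reach before consent are lesser matters of question wording and duplicate handling. The documents do not show that counts will be inflated.

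The conclusion assumes that the look-back is applied as written and that weeks run from baseline. If they ran from the first class, up to one week later, the pre-consent reach would be 2-5 weeks and the conclusion would not change. The change is worth making because the SAFTEE is the general systematic AE inquiry in both arms and a measure of a primary outcome.

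**What to change.** In protocol section 7.4, in DSMP section 3.2 and on the SAFTEE form, replace the fixed 8-10 week period with: *since the last completed SAFTEE (since the baseline SAFTEE if no follow-up SAFTEE has been completed)*. The baseline administration in Table 3 already supplies the starting point.

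The cost is one phrase in two sections and on the form, with no added visits or data items. The downside is longer recall after a missed visit (10, 13 or 18 weeks, as worked out above), and recall over 13 weeks is less reliable than over 8. That is still better than leaving those weeks unasked. The change cannot recover events in participants who never return.

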7.5 Reporting Procedures

Unanticipated Problem Reporting

Incidents or events that meet the OHRP criteria for unanticipated problems require the creation and completion of an unanticipated problem report form. OHRP recommends that investigators include the following information when reporting an adverse event, or any other incident, experience, or outcome as an unanticipated problem to the IRB:

- Appropriate identifying information for the research protocol, such as the title, investigator's name, and the IRB project number;
- A detailed description of the adverse event, incident, experience, or outcome;
- An explanation of the basis for determining that the adverse event, incident, experience, or outcome represents an unanticipated problem;
- A description of any changes to the protocol or other corrective actions that have been taken or are proposed in response to the unanticipated problem.

To satisfy the requirement for prompt reporting, unanticipated problems will be reported using the following timeline:

- Unanticipated problems that are serious adverse events will be reported to the IRB, SMC, and NCCIH within 7 days of the investigator becoming aware of the event.
- Any other unanticipated problem will be reported to the IRB, SMC, and NCCIH within 14 days of the investigator becoming aware of the problem.

All unanticipated problems should be reported to appropriate institutional officials (as required by an institution's written reporting procedures), the supporting agency head (or designee), and OHRP within one month of the IRB's receipt of the report of the problem from the investigator.

Adverse event reporting

SAEs that are unanticipated, serious, and possibly related to the study intervention will be reported to the Data Safety and Monitoring Board (DSMB), IRB, and NCCIH in accordance with requirements.

- Unexpected fatal or life-threatening AEs related to the intervention will be reported to the NCCIH Program Officer and DSMB within 3 days of the investigator becoming aware of the event. Other serious and unexpected AEs related to the intervention will be reported within 7 days.
- Anticipated or unrelated SAEs will be handled in a less urgent manner but will be reported to the SMC, IRB, and other oversight organizations in accordance with their requirements, and will be reported to NCCIH on an annual basis.
- All other AEs documented during the course of the trial will be reported to NCCIH on an annual basis by way of inclusion in the annual report and in the annual AE summary which will be provided to NCCIH and to the DSMB. The DSMB Report will state that all AEs have been reviewed.

